# **3.2** Rationale for study design, doses and control groups

The rationale for conducting this study in patients with COPD is given in Section 1.3. The rationale for the optional pharmacogenetics component of the study is included in Appendix D.

#### **3.2.1** Rationale for patient population and control groups

The patients with a  $FEV_1$  range of 40 - 70% predicted are selected for this study with the expectation that at these levels of  $FEV_1$  they will have sufficient airways disease detectable by CT and that be able to show a response to treatment, while avoiding patients with too severe disease who may deteriorate on withdrawal of ICS/LABA. To reduce the radiation risk only patients aged 50 years or above will be enrolled as older patients have a reduced risk of cancer from ionising radiation.

To minimise the variability that could occur as a result of patients being on different medications for COPD, all patients will be standardised to maintenance therapy with tiotropium.

To provide a comparator for the treatment effects of AZD9668 a placebo group is chosen as a standard design for estimating efficacy.

#### 3.2.2 Rationale for study design

The study will be randomised, placebo-controlled and double-blind to ensure a robust design and minimise bias, which could compromise the conduct of the study and/or interpretation of the results.

#### **3.2.3** Rationale for the selection of outcome variables

The end-points chosen as primary and secondary variables are those that could be expected to improve with an anti-inflammatory drug in airways disease.

#### **MSCT** variables

The airway wall thickness on inspiratory scan (AWT-Pi10), which represents the wall changes over the entire airway tree, is selected as the primary variable as similar measurements (such as Wall Area Percentage, WA%) have been shown to respond to anti-inflammatory treatment in obstructive lung disease like asthma in 12 weeks.

Wall changes in 5th generation airways have been shown to correlate well with lung function changes (Matsuoka S et al 2008, Coxson HO et al 2008a). Air Trapping on expiratory CT is known to correlate well with symptom scores and physiological air trapping (Lee YK et al 2008). Airway wall thickness and wall area % of airways from 4th (sub-segmental) to 6th generation airway tree will be evaluated to see any specific

changes related to small airways (Hasegawa M et al 2005, Hogg JC 2006). Lung density will be measured using a cut-off of -856HU, -910 HU and -950 HU on inspiratory scan to measure the extent of emphysema (Density mask method). The extent of emphysema will be represented as a percentage of lung that is emphysematous (relative area). Lung density will be measured using the histogram method to identify the extent of emphysema in the inspiratory scan over whole lung field. To accommodate for any small volume differences the PD15 values will be corrected for lung volume (Adjusted density = observed density x observed volume / predicted TLC) as described in Dirksen A 2008.

#### **3.2.4** Rationale for dose consideration and treatment duration

A dose of 60 mg twice daily has been chosen for this study since this is the highest dose expected to be well tolerated, whilst achieving steady state concentrations and is shown to produce 90% inhibition of zymosan stimulated NE activity in whole blood (based on previous study data), which is assumed to be directly related to the clinical effects.

A 3 month treatment duration is considered sufficient to show an effect on the primary and secondary variables (Capraz F et al 2007, Niimi A et al 2004), but will not apply to emphysema scores given the short study time frame.

# 4. **PATIENT SELECTION CRITERIA**

Investigator(s) should keep a record, the patient screening log, of patients who entered pre-study screening.

Each patient should meet all of the inclusion criteria and none of the exclusion criteria for this study. Under no circumstances can there be exceptions to this rule.

# 4.1 Inclusion criteria

For inclusion in the study patients should fulfil the following criteria:

- 1. Provision of informed consent prior to any study specific procedures at Visit 1a.
- 2. Male or female aged 50-80 years inclusive at Visit 1b. Female patients may be of non-childbearing potential (ie, post menopausal or surgically sterile) or of child bearing potential:
  - Women will be considered post menopausal if they are
     i) over 50 years old and have been amenorrheic for 12 months or more following cessation of all exogenous hormonal treatments or
     ii) over 57 years old

- Surgically sterile is defined as having undergone hysterectomy and/or bilateral oophrectomy and/or bilateral salpingectomy; tubal ligation on its own is not adequate
- Women will be considered of child bearing potential if they are between menarche and menopause, and have not been permanently or surgically sterilised. Women of child bearing potential must have a pregnancy test at Visit 1b and at Visit 2 prior to randomisation, and at the follow up visit, and must be using suitable methods of birth control. Further details of methods of birth control that are considered suitable for use are given in Section 5.1.
- 3. Documented clinical diagnosis of COPD, according to GOLD guidelines (GOLD 2008) with symptoms for  $\geq 1$  year before Visit 1b.
- 4. Ex-smokers for at least 12 months prior to Visit 1b.
- 5. A smoking history of at least 10 pack years (1 pack year = tobacco consumption corresponding to 20 cigarettes smoked per day for 1 year).
- 6. FEV1 40-70% (inclusive) of the predicted normal value (post-bronchodilator) at Visit 1b.
- 7.  $FEV_1/FVC < 70\%$  (post-bronchodilator) at Visit 1b.
- 8. Able to use the handheld electronic devices (assessed at Visit 1a).

# 4.2 Randomisation inclusion criteria (at Visit 2)

For randomisation into the study at Visit 2 the patients must also fulfil the following criteria:

- 1. MSCT performed during the last 2 to 7 days before randomisation with acceptable quality and the whole lung is visible on the images, as judged by the radiologist visual read.
- 2. No clinically relevant abnormal findings in baseline CT besides CT changes related to COPD, (eg, congestive heart failure, lung cancer, tuberculosis, lung fibrosis, sarcoidosis, cystic fibrosis) which in the opinion of the Investigator, may put the patient at risk because of his/her participation in the study, or may influence the results of the study, or the patient's ability to participate in the study.
- 3. Complete morning recordings of daily FEV1 data at least 10 days out of the last 14 days before Visit 2.

### 4.3 Exclusion criteria

Patients should not enter the study if any of the following exclusion criteria are fulfilled:

- 1. Any clinically relevant disease or disorder (eg, infectious/viral disease (including hepatitis B or C) cardiovascular, pulmonary other than COPD, gastrointestinal, liver, renal, neurological, musculoskeletal, endocrine, metabolic, malignant, psychiatric, major physical impairment), past or present, which in the opinion of the Investigator, may either put the patient at risk because of participation in the study, or may influence the results of the study, or the patient's ability to participate in the study.
- 2. Significant or unstable ischemic heart disease, arrhythmia, cardiomyopathy, heart failure, uncontrolled hypertension, or any other relevant cardiovascular disorder as judged by the Investigator.
- 3. Current diagnosis of asthma according to GINA guidelines (GINA 2008).
- 4. Malignancy or neoplastic disease within the past 5 years other than treated basal/squamous cell skin carcinoma or treated cervical cancer in situ.
- 5. Patients who require long term oxygen therapy (LTOT).
- 6. Worsening of COPD within 4 weeks prior to Visit 1b and during the run-in period (defined as an increase in respiratory symptoms requiring hospitalisation and/or a course of oral glucocorticosteroids and/or increased usage/dose of inhaled steroids and/or antibiotic treatment).
- 7. Acute infections requiring treatment in the 4 weeks prior to Visit 1b and during the run-in period.
- 8. Any clinically relevant abnormal findings in physical examination, vital signs, haematology, clinical chemistry, or urinalysis at Visit 1b, which in the opinion of the Investigator, may put the patient at risk because of his/her participation in the study, or may influence the results of the study, or the patient's ability to participate in the study.
- 9. A QTcB interval of >450 msec for males and >470 msec for females at Visit 1b.
- 10. Any ECG abnormality (including arrhythmia), which in the opinion of the investigator may put the patient at risk or interfere with study assessments at Visit 1b.

- 11. A past history of or current clinical or laboratory evidence of renal failure, or an estimated creatinine clearance of <50 mL/min (as calculated by the Cockcroft-Gault formula) at Visit 1b.
- 12. Alanine aminotransferase (ALT) and/or aspartate aminotransferase (AST) level  $\geq 1.5$  x upper limit of normal (ULN) at Visit 1b.
- 13. Pregnancy, breast-feeding or planned pregnancy during the study.
- 14. Involvement in the planning and/or conduct of the study (applies to both AstraZeneca staff and/or staff at the study site).
- 15. Previous randomisation to treatment in the present study.
- 16. Previous participation in a study with AZD9668.
- 17. Participation (defined as administration of at least 1 dose of investigational product) in another clinical study, the last follow-up visit of which is within 12 weeks of Visit 1b in this study.
- 18. Excessive alcohol consumption or known drug abuse, as judged by the investigator.
- 19. Scheduled in patient surgery or hospitalisation during the course of the study.
- 20. Patients scheduled for an intensive COPD rehabilitation programme. (Patients who are in the maintenance phase of a rehabilitation programme are eligible to take part.)
- 21. Known or suspected hypersensitivity to the investigational product or excipients or additional non-investigational study drugs provided for the study (tiotropium and reliever medication).
- 22. Patients with conditions that may worsen if treated with tiotropium, according to the prescribing information for tiotropium in each participating country.
- 23. Patient with an unremovable metallic object in the chest area (including piercing, pacemakers, stents).
- 24. Patient with a history of lung/cardiothoracic surgery in the past (lung volume reduction surgery, lung transplant, bypass etc.).
- 25. MSCT performed during the last 9 months before Visit 1b.

26. Presence of 1 or more non-calcified lung nodules with diameter  $\geq$ 5 mm, identified from baseline MSCT scan.

Exclusion criteria for the pharmacogenetic part of the study are specified in Appendix D.

Procedures for withdrawal of incorrectly enrolled patients are described in Section 5.3.

# 5. STUDY CONDUCT

## 5.1 **Restrictions during the study**

The following restrictions apply:

- Use of disallowed concomitant medication (refer to Section 5.6.3)
- All female patients must have a serum pregnancy test at Visit 1b and Visit 7. Women of child bearing potential must undergo an additional urine pregnancy test at Visit 2 prior to randomisation. Women of child bearing potential must be using highly effective methods of birth control:
  - Total sexual abstinence. Abstinence must be for the total duration of the study.
  - Vasectomised sexual partner (with participant assurance that the partner received post-vasectomy confirmation of azoospermia).
  - Tubal occlusion

٠

- Intra-uterine device (coils must be copper banded)
- Intra-utrine system (IUS) (Levonorgestrel IUS eg, Mirena)
- Medroxyprogesterone injections (Depo-provera)
- Prior to the clinic lung function tests:
- No alcohol within 4 hours
- No vigorous exercise within 2 hours
- No large meals within 2 hours
- No prohibited medication as listed in Section 5.6.3.1

The patient should not start smoking during the study.

- Patients should not donate blood at any time during the study or for 3 months following completion of the study.
- Patients should abstain from taking part in any other study, whilst participating in this study.

# 5.2 Patient enrolment and randomisation

The Principal Investigator will:

- 1. Obtain signed informed consent from the patient before any study specific procedures are performed.
- 2. Assign the patient a unique enrolment number, beginning with "E0001001 (EXXXXYYY)" where XXXX reflects the centre number and YYY will be allocated sequentially to enrolled patients at each centre
- 3. Determine patient eligibility. See Sections 4.1, 4.2 and 4.3.
- 4. Assign eligible patient unique randomisation code (patient number) at Visit 2.

Re-enrolment is allowed only if enrolment has failed due to technical problems, eg, with the eDiary. Patients failing to meet an inclusion or meeting an exclusion criterion must not re-enter the study. If a patient discontinue the study after randomisation he/she can not re-enter the study.

If a patient withdraws from participation in the study, then his/her enrolment/randomisation code cannot be reused. Patients who discontinue the study after randomisation will not be replaced.

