The total radiation dose for the study is expected to be around 10 - 12 mSv. This dose is close to accepted radiation dose for biological research (1 to 10 mSev). In the present study the radiosensitive group has been therefore excluded to a major extent. The older demographic of patients fall into a low risk profile for risk of radiation, and the laboratory safety results from Visit 1b must be reviewed and considered eligible prior to baseline scan to avoid any unnecessary radiation exposure. The selection of patients includes male and female patients aged 50 - 80 years. Each patient will receive 4 scans, 2 scans (a paired inspiratory and expiratory scan) at each visit, 3 months apart. The imaging protocol and study design is based on the EU guidance (See Guidance document). The potential benefits of the study are expected to be Category IIB (aimed directly at the diagnosis, cure or prevention of disease). Since this is a study to establish the feasibility of a clinical trial in COPD evaluated by MSCT the study has not been adequately powered to demonstrate efficacy but only to detect a trend.

The study design chosen for this study is considered to optimal to detect a clinically meaningful effect of AZD9668 while the safety risks are minimised. The benefit/risk balance of using AZD9668 in the present study in patients with COPD can therefore be considered acceptable.

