### PEF

Measurements of PEF in the morning and in the evening, expressed in L/min, will be performed from the evening of Visit 1b to the morning of Visit 6. The patient will be requested to perform 3 manoeuvres twice daily (morning and evening). The measurements should be done upon rising in the morning before intake of morning dose of tiotropium and investigational product but after clearing out mucus. Patients should also refrain from taking their reliever medication prior to the morning measurements if possible. Evening measurements to be performed before bedtime. The measurements should be made while standing. The patient should use the same handheld spirometer during the entire study. Data from the PEF recordings are transferred to a database at the clinic visits.

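### No diary check is scheduled before the baseline CT, so a patient who can no longer be randomised may be scanned, and that scan then closes the re-enrolment route for eDiary problems

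*Protocol*

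**What the plan says.** **Diary criterion.** Protocol 4.2, criterion 3, is assessed at Visit 2 and requires complete morning FEV1 "data at least 10 days out of the last 14 days before Visit 2". Section 6.3.8 does not allow missed entries to be filled in afterwards.

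**When the site sees the diary.** The device is dispensed at Visit 1b. Table 2 schedules the next check at Visit 2, and Table 1 has no clinic visit between the two. Section 6.3.5 says of the home measurements, from which FEV1 is also read: "Data from the PEF recordings are transferred to a database at the clinic visits".

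**Baseline scan.** Section 4.2, criterion 1, requires "MSCT performed during the last 2 to 7 days before randomisation with acceptable quality". Sections 3.1 and 6.3.1 make the scan wait for the Visit 1b laboratory results. Neither mentions the diary.

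**Re-enrolment.** Section 5.2: "Re-enrolment is allowed only if enrolment has failed due to technical problems, eg, with the eDiary". Its next sentence reads: "Patients failing to meet an inclusion or meeting an exclusion criterion must not re-enter the study".

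**Exclusion 25 (4.3).** "MSCT performed during the last 9 months before Visit 1b". Scans done for this study are not exempted, and section 4 says of the criteria: "Under no circumstances can there be exceptions to this rule".

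**Radiation.** Section 1.4: "The total radiation dose for the study is expected to be around 10 - 12 mSv". This covers four scans in two inspiratory/expiratory pairs and is set beside a reference range of 1 to 10 mSv. The same section gives the avoidance of needless exposure as the reason for reviewing the laboratory results first.

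**The concern.** The scan is the study procedure with a radiation cost, and it is placed before the only scheduled look at a criterion that may already have failed. The laboratory check exists so that patients who cannot go on are not irradiated. The same reasoning applies to the diary, but no equivalent check is planned.

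The second issue is what happens next. The one example that 5.2 gives for permitted re-enrolment is an eDiary problem. If the problem is noticed at Visit 2, the patient already has a study scan, and exclusion 25 applies at any new Visit 1b. The protocol does not say whether a study scan counts under exclusion 25, so sites must work out for themselves whether the allowance can be used. At stake are avoidable exposure, the loss of otherwise suitable patients, and inconsistent handling across about 15 centres.

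**Working it through.** **1. When criterion 3 becomes unreachable.** The requirement is 10 of 14 mornings, so 14 − 10 = 4 may be missed and the fifth miss is decisive for that Visit 2 date. If the window is counted as days −14 to −1, five consecutive misses from the start fall on days −14 to −10. The point can thus be reached by day −10, before the earliest scan day (day −7).

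One refinement: the run-in may last 14 to 17 days (Table 1), so a Visit 2 planned at 14 days can move by 17 − 14 = 3 days. That drops at most three missed mornings from the window. Five to seven misses might therefore be recovered by moving the visit; eight or more cannot.

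**2. Where the scan falls.** With a 14-day run-in the scan is on day 14 − 7 = 7 to 14 − 2 = 12 of the run-in. With a 17-day run-in it is on day 10 to 15. In every case it precedes the Visit 2 diary check.

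**3. Dose.** The stated 10 to 12 mSv cannot be rebuilt, because no dose per scan is given. Assuming that each pair carries half:
- one pair: 10/2 = 5 to 12/2 = 6 mSv
- three pairs: 3 × 5 = 15 to 3 × 6 = 18 mSv, 50% above plan.

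**4. Can the first scan be reused after re-enrolment?** If a new run-in starts on the day of the failed Visit 2, the scan's age at the new Visit 2 is its age at the failed visit (2 to 7 days) plus the new run-in (14 to 17 days): 2 + 14 = 16 to 7 + 17 = 24 days. Even with only 10 new diary days it is at least 2 + 10 = 12 days old. The limit in 4.2 is 7 days, so a new baseline pair would be needed and the Visit 6 pair would be the third.

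**5. Can exclusion 25 be waited out?** Take the earliest case: Visit 1b on 1 January 2010, Visit 2 on 15 January, scan on 8 to 13 January. Nine months later the new Visit 1b is 8 to 13 October, and Visit 2 (14 days on) is 22 to 27 October. Visit 7 at 14 weeks less 3 days (95 days) is 25 to 30 January 2011. Section 9.5 plans the end by Q4 2010.

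**6. Illustration only.** The protocol gives no device failure rate. Assume that each morning is recorded independently with probability p. With the scan at day −7, −4 or −2, 7, 10 or 12 of the 14 mornings have passed. The probability that at least five are already missed is the binomial upper tail with miss probability 1 − p:

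| Assumed p | Day −7 | Day −4 | Day −2 |
|---|---|---|---|
| 0.5 | 0.227 | 0.623 | 0.806 |
| 0.3 | 0.647 | 0.953 | 0.991 |

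For p = 0.5 and 7 mornings: (21 + 7 + 1)/128 = 0.227. A real fault would tend to persist from day to day, so independence is doubtful. The table shows only that, with a poorly recording device, a check before the scan would often find the problem in time.

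**The case against.** The strongest defence is that the rules can be read together. Permission given only if a technical problem occurred is a necessary condition, not a guarantee of eligibility. A re-enrolled patient must still meet every criterion, so a fault before the scan permits re-enrolment and a fault after it does not. That stands: the protocol can be followed without contradiction.

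A reader might infer that the ban on re-entry in 5.2 is a further conflicting rule, because missing criterion 3 is failing an inclusion criterion. The documents do not support this firmly. The technical-problem sentence comes immediately before the ban and reads naturally as its exception, and 4.2 is headed separately from the inclusion criteria in 4.1.

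A reader might also infer that diary faults always come to light only at Visit 2. That goes too far. Sections 6.3.5 and 6.3.8 tell patients where to get help with the device, and 1.4 speaks of close monitoring with daily measurements during run-in. A device that is dead from the start could well be reported before the scan. What remains is that this depends on the patient or on monitoring that is not described. Section 6.2 speaks of scanning eligible patients, but criterion 3 is assigned to Visit 2.

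Finally, any scan-based eligibility rule leaves some patients scanned and not randomised; 4.2 criteria 1 and 2 and exclusion 26 do so unavoidably. The diary case differs because the failure can be visible before the scan.

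**Conclusion.** The point holds as a modest, cheaply corrected weakness in design. Followed as written, the plan can expose a patient to about 5 to 6 mSv when randomisation at that attempt is already impossible. The scan then makes the 5.2 re-enrolment allowance unusable within the planned study period.

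A reader might infer that the protocol leads to a third scan pair and 15 to 18 mSv. It does not: that follows only if a site lets 5.2 override exclusion 25, which section 4 forbids. The figure is the cost of misreading an unclear text, not of following the plan.

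The dose figures assume an equal split between the two scan pairs. The number of patients concerned is unknown. About 70 are to be enrolled for 50 randomised, so about 20 are expected to be lost for all reasons, and technical failures noticed after the scan are an unquantified part of those. The primary analysis, power and randomisation are not touched.

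**What to change.** 1. In 3.1, 4.2 and 6.3.1, add a diary and device check before the baseline MSCT, by phone or with the device in hand. Do not scan a patient who can no longer reach 10 of 14 mornings on any Visit 2 date that the schedule allows. Checking before the scan also lets the site move Visit 2 and the scan together where the run-in window permits.
2. Reconcile 5.2 with exclusion 25 and with 4.2 criterion 3. State whether a study scan counts under exclusion 25, whether re-enrolment is possible after the baseline scan, and whether a diary shortfall caused by a device fault falls under the re-entry ban. If re-enrolment after the scan is to be possible, the dose statement in 1.4 must be brought into line. Which rule prevails is for the sponsor to decide.

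The cost is a few sentences of protocol text and one extra phone or device check per patient. A fault that arises between the check and Visit 2 would still be missed.
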